12.0 Procedures Involved*

12.1 Provide a description of *all research procedures or activities* being performed and when they are performed once a subject is screened and determined to be eligible. Provide as much detail as possible.

NOTE: This should serve as a blueprint for your study and include enough detail so that another investigator could pick up your protocol and replicate the research. For studies that have multiple or complex visits or procedures, consider the addition of a schedule of events table in in your response.

Response: Because of the highly contagious nature of COVID infection in the first few days after onset of symptoms, it is essential to minimize exposure of research team members to the subjects. Therefore, except for the enrollment visit, all procedures for this study will be conducted remotely at the subject's home. The Table below depicts all the research procedures.

	Screen	Enrollment							
Day +/- Window	-1 or 1	1	Daily until	Daily until	Day 3 ± 1	Day 7 ± 1	Day 14 ± 2	Day 28 ± 3	Day 42 ± 3

			day 14	day 42					
Assessments/Procedures									
ELIGIBILITY									
Informed consent	X								
Demographics & Medical History	X								
Prior SARS-CoV-2 based on screening or perform rapid antigen testing	X								
STUDY INTERVENTION									
Randomization		X							
Administration of Melatonin/Placebo		X	X						
STUDY PROCEDURES									
Body temperature		X	X	X	X	X	X	X	X
Clinical data collection		X	X	X	X	X	X	X	X
Pulse Oximetry measurement		X	X	X	X	X	X	X	X
Adverse event evaluation		X			X	X	X	X	X
RESEARCH LABORATORY									
Saliva for PCR SARS-CoV-2		X			X	X	X	X	X
Saliva for Cytokine/Chemokine RNA and/or protein		X			X	X	X	X	X

Below is a day by day description of the study procedures.

- For those subjects that have not had a COVID-test: Subjects will be enrolled and then tested for SARS-CoV2 using an EUA rapid antigen administered by the study team. If negative by rapid antigen test subjects will be withdrawn from study. Those subjects that have a prior positive test will not be give a rapid antigen test.
- If COVID-19 positive:
- Collect a baseline sample of saliva prior to taking drug, by spitting in a collection container that will be provided at time of consent.
- Rate COVID symptoms before starting medication and then each day in the evening on a short questionnaire from Day 1 to Day 42.
- Record body temperature and pulse oximetry each day in the morning and evening.

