19.0 Data Management and Analysis*

19.1 *Describe the data analysis plan, including any statistical procedures. This section applies to both quantitative and qualitative analysis.*

Response:

Randomization: Participants will be randomized to the intervention or control arm in a 2:1 fashion using a permuted block randomization scheme. The randomization lists to be used in this study will be generated by the study biostatistician. Subjects will be included in data analyses according to their randomized assignment irrespective of the treatment actually received (intent-to-treat).

Missing data: The amount and nature of missing data will be characterized and no method of imputation will be used for missing data. We acknowledge the possibility of informative missingness with some of the outcomes, that is, the probability of a particular observation being missing may be related to the health or death of a subject, and therefore analyses will be interpreted with caution.

Accrual: Participants will be accrued to the study on a first-come basis. The projected accrual is approximately 15 per month, and therefore recruitment is expected to be complete at most 60 days following the study starting point. Subjects will be followed for 1 month after recruitment completion, so total study duration will be approximately 3 months. During the enrollment period, the study biostatistician will model and predict accrual rates in order to verify adequacy of the enrollment process.

Descriptive analyses: Measured outcome variables will be summarized overall and by relevant demographic and baseline variables. Descriptive statistics such as frequencies and relative frequencies will be computed for all categorical variables. Numeric variables will be summarized using simple descriptive statistics such as the mean, standard deviation and range. A variety of graphical techniques will also be used to display data, ex., histograms, boxplots, scatterplots, etc.

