Statistical analyses: Analyses will be performed with a focus on estimation of specific clinically important parameters, including preliminary evidence of safety and activity of the intervention, for use in the planning of subsequent comparative trials designed to fully assess safety and efficacy. The primary outcomes in the examination of the study intervention, specifically, the cumulative incidence of serious adverse events (SAEs), the cumulative incidence of Grade 3 and 4 adverse events (AEs), and the discontinuation or temporary suspension of the investigational medication (for any reason), are measured in a binary fashion at the

study participant-level. The corresponding probabilities will each be estimated using the relative frequency. In addition to the point estimates based on collected data, 95% confidence intervals will also be computed based on the methodology of Clopper and Pearson. Additional binary study outcomes, ex., incidence of COVID-related hospitalization and hospitalization for any reason, will be analyzed in an identical fashion. Comparison between randomized groups with regards to these outcomes will be done using Fisher's exact test. For numeric outcomes, such as symptom questionnaire results and measures of clinical improvement, the rank-based Wilcoxon rank sum test will be used to compare groups. For outcomes which may be subject to censoring such as speed of resolution of COVID related symptoms, parameter estimation will be based on the Kaplan-Meier estimator and the log-rank test will be utilized to compare groups. Proposed exploratory outcomes are collected longitudinally. Proposed exploratory outcomes are collected longitudinally. Standard statistical techniques for the analysis of such outcomes, ex., mixed linear models, will be utilized. Although primary analyses will be performed based on the intent-to-treat principle, to evaluate the robustness of these results, analyses will also be conducted in a secondary fashion based on actual treatment received. All statistical tests will be two-sided and tested at a 0.05 nominal significance level. All analyses will be carried out using SAS version 9.4 (or higher) statistical software (Cary, NC).

19.2 *If applicable, provide a power analysis.*

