NOTE: This may not apply to certain types of studies, including chart/records reviews, survey studies, or observational studies. This question is asked to elicit whether the investigator has an adequate sample size to achieve the study objectives and justify a conclusion.

Response:

Sample size justification: In that accurate assessment of the safety of the study intervention is of utmost importance in this study, the sample size of 20 in the intervention group is based on the expected precision associated with our estimated safety probabilities corresponding to the primary outcomes expressed in terms of confidence interval width. Note that a true probability of 0.5 represents the mathematically worst-case scenario with regards to precision and therefore we may take precision at that point to be an upper bound of expected accuracy. We see that with a sample size of 20 participants the standard error of these estimators will be at most 11 percentage points.

19.3 *Describe any procedures that will be used for quality control of collected data.*

Response: Collected data will be reviewed by the co-PIs on a weekly basis to ensure adequate data collection.

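### Section 19.1 names an unqualified log-rank test for the secondary symptom endpoint; read as the chi-square version at 20 v 10, its two-sided error is about 6% rather than 5%, with the excess towards melatonin looking slower (minor).

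*Combined protocol and SAP*

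**What the plan says.** Section 19.1 (Statistical analyses) handles outcomes that may be censored, with speed of symptom resolution as its example, by stating that "parameter estimation will be based on the Kaplan-Meier estimator and the log-rank test will be utilized to compare groups". The level is set for every test: "All statistical tests will be two-sided and tested at a 0.05 nominal significance level". The software is SAS 9.4 or higher, and no option for the log-rank p-value is given.

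For binary outcomes the same paragraph does choose small-sample methods: Clopper-Pearson intervals, and for the comparison of arms "Comparison between randomized groups with regards to these outcomes will be done using Fisher's exact test".

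On allocation, 19.1 (Randomization) says "Participants will be randomized to the intervention or control arm in a 2:1 fashion using a permuted block randomization scheme". Section 1.0 gives a total of 30, and in 19.2 "the sample size of 20 in the intervention group is based on the expected precision", so the comparison is 20 v 10. On timing, the instruction in 12.1 is "Rate COVID symptoms before starting medication and then each day in the evening on a short questionnaire from Day 1 to Day 42". Sections 1.0 and 3.0 place speed of resolution among the secondary objectives.

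**The concern.** The usual log-rank p-value refers a standardized statistic to a chi-square distribution, which is a large-sample approximation. With 10 subjects in the smaller arm the approximation may be off, and with unequal arms its two tails need not be equal. The plan protects its binary comparisons against this and leaves the time-to-event comparison unprotected.

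At stake is whether the stated 0.05 is delivered for this comparison, and whether the error leans one way. The plan wants preliminary evidence of activity for planning later trials. An error leaning towards slower recovery on melatonin could discourage follow-up without cause.

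**Working it through.** **The plan's own figure.** Section 19.2 gives a maximum standard error for a proportion with 20 subjects: √(0.5 × 0.5 / 20) = 0.112, which is the stated 11 points after rounding. It confirms the arm size but says nothing about the log-rank test. No power or error rate is given for that test beyond the nominal level.

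**Inputs from the documents.** 20 v 10; daily ratings to Day 42, so censoring at Day 42; two-sided 0.05.

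**Inputs assumed, because the documents give none.** Exponential resolution times with the same distribution in both arms and medians from 5 to 40 days; dropout of 0% or 10%.

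**Statistic.** On day t let n be the number still at risk, n₁ those of them on melatonin, d the number resolving and d₁ those of them on melatonin. Then

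- U = Σ (d₁ − d·n₁/n)
- V = Σ d·(n₁/n)·(1 − n₁/n)·(n − d)/(n − 1)
- reject if |U/√V| > 1.96; a negative value means melatonin looks slower.

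**Simulated error under no effect, daily times**

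| Arms | Assumed median (days) | Two-sided | Melatonin slower | Melatonin faster |
|---|---|---|---|---|
| 20 v 10 | 7 | 6.2% | 3.7% | 2.4% |
| 20 v 10 | 10 | 6.2% | 3.8% | 2.4% |
| 20 v 10 | 14 | 6.0% | 3.7% | 2.3% |
| 20 v 10 | 20 | 5.7–5.8% | | |
| 20 v 10 | 40 | 5.3–5.4% | | |
| 15 v 15 | 7 to 14 | 5.8–6.0% | tails equal | |
| 10 v 5 | 7 to 14 | 6.8–6.9% | 4.3–4.4% | 2.4–2.5% |
| 10 v 5 | 40 | 5.5–5.7% | | |

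The 20 v 10 rows for medians of 7 to 14 days used 400,000 replicates, so the simulation standard error is √(0.062 × 0.938 / 400,000) = 0.0004, or 0.04 points. With 10% dropout the 20 v 10 figure is 6.1 to 6.2%. The statistic matched a standard library routine on five data sets, and 200 v 100 gave 5.2% (10,000 replicates), so the excess is a sample-size effect and not a coding error.

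**Where it comes from.**

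- *Sample size.* 15 v 15 also gives about 6%, so the total excess is due to small numbers.
- *Allocation.* The tails are equal at 15 v 15 and unequal at 20 v 10, so the lopsidedness is due to 2:1. The ratio of the tails is about 3.7 / 2.3 = 1.6.
- *Daily ties.* Continuous times gave 6.2% against 6.1% for daily times at median 7, and 6.1% for both at median 14. Ties contribute nothing.

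**Does a permutation p-value repair it?** Give each subject the log-rank score (1 if resolved, 0 if censored) − Σ d/n over days up to that subject's own time. The scores summed over the melatonin arm equal U. Re-randomize the arm labels with arm sizes fixed.

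- Two-sided p-value from the absolute score sum: the total returns to 5%, but the imbalance reverses. It is about 1.9% slower v 3.1% faster at 20 v 10 (1.9 + 3.1 = 5.0), and 1.2% v 3.6% at 10 v 5 (4.8 in total).
- Two-sided p-value as twice the smaller one-sided value: about 2.5% in each tail.

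A repeat of both permutation versions agreed to within 0.3 points.

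**The case against.** The case for leaving the plan alone is fair. The plan names a standard test in a standard way. The chi-square p-value is inferred from silence. No resolution time is documented, and slow resolution shrinks the excess to a few tenths of a point. The endpoint is secondary, the stated emphasis is on estimation, the level is called nominal, the sample size rests on the precision of safety estimates, and no decision rule hangs on this p-value. All of this stands, and it is why the point is minor. It does not make 0.05 the level delivered under the ordinary reading.

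Readers might infer three stronger things that the documents and the check do not support:

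- *That false claims of efficacy are inflated.* They are not: the faster tail stays at 2.2 to 2.4% for medians of 7 to 14 days, below its nominal 2.5%.
- *That the error is 7% or more.* That needs each symptom tested separately, only in those who have it, with half or fewer affected. Section 3.0 lists 13 symptoms but gives no prevalence and no such analysis rule.
- *That daily rating or the 2:1 split causes the excess.* Ties add nothing, and the split explains only the direction.

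One further objection stands against the remedy. A permutation p-value is strictly exact only if censoring is alike in both arms, and 19.1 itself expects that missingness may be related to health, while 22.1 allows withdrawal for drug-related events.

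**Conclusion.** The concern holds as a minor point. If the unqualified log-rank test means its large-sample version, the two-sided error at 20 v 10 is about 6% for assumed medians of 7 to 14 days and about 5.3% at a median of 40 days. If symptoms are analysed separately in affected subjects, which is not stated, it is about 7% at 10 v 5. The excess over 5% is 1.0 to 1.2 points, about one extra false signal in 80 to 100 trials with no effect (1/0.012 = 83; 1/0.010 = 100), and it points towards slower recovery on melatonin. The result rests on assumed exponential resolution times and on the ordinary reading of the test's name. It does not touch the primary safety analyses or the Kaplan-Meier estimates.

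**What to change.** Add one sentence to 19.1: the log-rank p-value will be taken from the permutation distribution of the log-rank scores over the 2:1 allocation, exact or with at least 10,000 Monte Carlo draws, and the two-sided p-value will be twice the smaller one-sided p-value. The last clause matters, because a p-value from the absolute score sum would raise the false-benefit tail to about 3.1%. Keep the Kaplan-Meier estimates as planned.

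This brings the comparison into line with the exact methods already chosen for binary outcomes and changes nothing in design, data collection or sample size. The costs are a few lines of code, slightly larger p-values in the slower direction, and a caveat that exactness assumes similar censoring in both arms. Reporting follow-up and dropout by arm would let a reader judge that.

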3.0 Scientific Endpoints*

2.1 Describe the scientific endpoint(s), the main result or occurrence under study.

*NOTE: Scientific endpoints are outcomes defined before the study begins to determine whether the objectives of the study have been met and to draw conclusions from the data. Include primary and secondary endpoints. Some example endpoints are: reduction of symptoms, improvement in quality of life, or survival. Your response should **not** be a date.*

Response:

Primary Objective

Evaluate the safety of the intervention through 42 days of follow-up as compared to the control arm as assessed by:

- Cumulative incidence of serious adverse events (SAEs)
- Cumulative incidence of Grade 3 and 4 adverse events (AEs).

- Adverse Events of Special Interest
- Discontinuation or temporary suspension of the investigational medication (for any reason).

Secondary Objectives

Evaluate the clinical efficacy of melatonin as compared to placebo as assessed by:

Hospitalization: Incidence of COVID related hospitalization at 42 days.

Data will be obtained from electronic medical record.

COVID related symptoms: Fever, chills, cough, nasal symptoms, body aches/muscle aches, headache, loss of smell, loss of taste, nausea, vomiting, diarrhea, fatigue, dizziness. The speed of resolution of COVID related symptoms. Change from baseline, Day 1 to Day 42. Accessed by questionnarre.

Change in the WHO Clinical Progression Scale (0-10). Data will be obtained from electronic medical record.

Mortality: 42-day mortality. Data will be obtained from electronic medical record.

Exploratory Objective

Evaluate the effect of melatonin on virologic parameters as compared to placebo and assessed by:

-Percent of subjects with SARS-CoV-2 detectable in saliva sample at days 1, 3, 7, 14, 28 and 42.

-Quantitative RT-PCR for SARS-CoV-2 virus in saliva sample at days 1, 3, 7, 14, 28 and 42.

-Evaluate the reduction in cytokine/chemokine RNA and/or protein levels in saliva:

-Reduction as compared to baseline (Day 1) in salivary levels of cytokine/chemokine RNA and/or protein (IL-1, IL-2, IL-3, IL-4, IL-6, IL-8, IL-10, IL-11, IL-12, IL-13, IL-17, IL-18, TNF α , IFNy, IFN α , IFN-B, MCP1) at days 3, 7, 14, and 28.

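### The log-rank comparison of speed of symptom resolution leaves out the pre-dose symptom rating; adjusting for it is a cheap efficiency gain for a secondary outcome, not the repair of an error.

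*Combined protocol and SAP*

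**What the plan says.** Section 3.0 lists, among the secondary objectives, "The speed of resolution of COVID related symptoms. Change from baseline, Day 1 to Day 42". It stands beside hospitalization, the WHO Clinical Progression Scale and mortality, with no ranking. For outcomes of this kind that may be censored, section 19.1 states that "parameter estimation will be based on the Kaplan-Meier estimator and the log-rank test will be utilized to compare groups". Numeric symptom questionnaire results are compared separately by the Wilcoxon rank sum test. Mixed models are reserved for the exploratory outcomes.

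Section 12.1 asks subjects to "Rate COVID symptoms before starting medication and then each day in the evening on a short questionnaire from Day 1 to Day 42", so a rating that treatment cannot have affected is scheduled for everyone. In section 19.1, baseline variables appear only in the descriptive summaries. Allocation is "randomized to the intervention or control arm in a 2:1 fashion using a permuted block randomization scheme", with no stratification factor named. On error rates the plan says "All statistical tests will be two-sided and tested at a 0.05 nominal significance level". In section 19.2, "the sample size of 20 in the intervention group is based on the expected precision" of the safety probabilities; no efficacy power, hazard ratio or event count is given.

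**The concern.** Section 8.1 admits mild or moderate disease with symptom onset within 5 days, so symptom burden on Day 1 can differ a good deal between subjects. If subjects who start with more symptoms take longer to clear them, part of the spread in resolution times is predictable from a value the trial already collects. The planned test treats that spread as noise. With 10 subjects expected on placebo, chance differences in Day 1 burden also pass straight into the comparison.

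At stake are some power in the two-sided test and the usefulness of the result for the stated aim of 19.1, which is to inform the planning of later comparative trials. Prespecifying the adjustment would also avoid having to choose one after an imbalance has been seen.

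**Working it through.** **The plan's own figure.** The only sample-size figure is a standard error of at most 11 percentage points with 20 subjects: sqrt(0.5 × 0.5 / 20) = 0.1118, or 11.2 points, which rounds to 11. It concerns the safety probabilities and says nothing about symptom resolution.

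**Inputs from the documents.** 30 subjects (1.0, 7.1), 20 of them on intervention (19.2) and so 10 on placebo at 2:1; two-sided 0.05 and the log-rank test (19.1); daily ratings to Day 42 (12.1).

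**Assumed inputs, not in the documents.** Placebo median 10 days; SD of log time 0.7; lognormal or Weibull times; no dropout; Day 1 symptom count between 1 and 13; correlation rho between Day 1 burden and log time of 0 to 0.5. The model is log T = log 10 + 0.7 × (rho × X + sqrt(1 − rho²) × e) − delta × arm, with X the standardized Day 1 burden. The time ratio is exp(−delta): 0.74 for delta 0.3 (26% shorter), 0.61 for 0.5 (39% shorter) and 0.50 for 0.7 (50% shorter).

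**Tests compared.** The plain log-rank test, and the log-rank scores (martingale residuals under the null) after regression on the Day 1 count. Both take p-values from random 2:1 re-allocation. The re-allocation was unrestricted, because the block size is not given.

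**Simulated power, plain to adjusted**

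| Correlation | Shortening | Lognormal | Weibull |
|---|---|---|---|
| 0.5 | 26% | 18.6% to 21.2% | 25.7% to 29.6% |
| 0.5 | 39% | 42.8% to 49.3% | 54.1% to 63.8% |
| 0.5 | 50% | 67.1% to 74.9% | 79.5% to 87.7% |
| 0.3 | 39% | 41.7% to 42.7% | 58.1% to 61.5% |
| 0.3 | 50% | 69.2% to 70.1% | 84.1% to 85.8% |
| 0 | 39% | 41.8% to 41.0% | 61.9% to 60.2% |
| 0 | 50% | 68.5% to 66.5% | 86.6% to 85.8% |

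Rejection under the null was 4% to 6% for both tests. Repeat runs, with simulation error of about 1 point, put the gain at correlation 0.5 at about 1 to 6 points for a 26% shortening and about 5 to 11 for 39% or 50%. The gain at correlation 0.3 was about 0 to 3 points, and the loss at correlation 0 at most about 2 to 3.

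**Cross-check by formula.** Schoenfeld power with allocation 2/3 is Phi(sqrt(D × 2/9) × log HR − 1.96) for D events. As an approximation to adjustment at correlation 0.5, divide the variance term by 1 − 0.5² = 0.75. With D = 30 and HR 2: sqrt(6.667) × 0.693 − 1.96 = −0.17, giving 43.2%; adjusted, sqrt(8.889) × 0.693 − 1.96 = 0.11, giving 54.2%, a gain of 11.0 points. With 30 events the gain is 1.5 points at HR 1.25, 4.6 at HR 1.5, 12.2 at HR 2.5 and 3.8 at HR 4. It is always a gain, but its size depends on the effect assumed.

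**Choice of adjusted test.** In a separate simulation (Weibull, placebo median 14 days), adjusting with a Cox Wald test at correlation 0 cost about 3 to 7 points for HR 1.5 to 4. A likelihood-ratio test cost about 0 to 3. This favours the re-randomized score test over a Wald test at this sample size.

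**Chance imbalance.** The SD of the difference in mean Day 1 burden between arms is sqrt(1/20 + 1/10) = 0.387 SD. Then 0.5 / 0.387 = 1.29, so the chance of a difference of at least 0.5 SD in either direction is 19.7%.

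**The case against.** The strongest reply is that power is not this plan's criterion. Section 19.1 puts estimation first, 19.2 sizes the trial on safety precision, and 2.1 leaves the efficacy question to a later, adequately powered study. That stands: no stated figure is wrong, and the planned test is valid. The 19.7% chance of imbalance is ordinary variation that the type I error already allows for. It does not follow that the rating should go unused, since 19.1 still tests at 0.05 and wants preliminary evidence of activity for planning.

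A reader might infer that this is the main symptom efficacy comparison and that the plan forfeits a definite 6 to 10 points of power. The documents support neither. The endpoint is unranked, and symptom scores are also compared by Wilcoxon test. A band of 6 to 10 points needs both a correlation near 0.5 and a large shortening, and the documents give neither. With a 26% shortening power is low under either test, and at correlation 0.2 or below the gain is about nil or negative.

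Two practical objections also stand. Changing only the p-value would leave the planning estimates unadjusted, so an adjusted estimate is needed. Further, 19.1 rules out imputation, so a subject without a Day 1 rating leaves the adjusted test. With 3 of 30 ratings missing at random (an assumption), the adjusted test on the remaining 27 was about 0 to 4 points worse than the plain test on all 30 at correlation 0.3, and between no change and 5 points better at 0.5.

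Finally, the questionnaire is an attachment not seen here, and the text does not say whether resolution means all symptoms or each one. The assumed 1 to 13 count therefore cannot be checked.

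**Conclusion.** The point holds as a modest, inexpensive improvement to a secondary analysis. The log-rank comparison ignores a scheduled pre-dose rating that may well be prognostic, and nothing else in the documents brings that rating into this comparison. On the assumptions above, adjustment is worth about 1 to 11 points of power at correlation 0.5 for a 26% to 50% shortening and about 0 to 3 points at correlation 0.3; it costs up to about 2 to 3 points at correlation 0. The direction is secure if Day 1 burden is at least moderately related to resolution time. The size cannot be fixed from the documents.

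**What to change.** In section 19.1:

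- Keep the Kaplan-Meier curves.
- Make the between-group test for speed of symptom resolution a log-rank-score test adjusted for the pre-dose Day 1 symptom rating, or for that symptom's own Day 1 rating if symptoms are analysed singly. Take the p-value by re-randomization that follows the 2:1 permuted blocks.
- Report a Day 1-adjusted effect estimate with its 95% confidence interval, such as a hazard ratio or time ratio. An adjusted hazard ratio is conditional on Day 1 burden and should be labelled so.
- Keep the unadjusted log-rank test on all randomized subjects as a sensitivity analysis.
- Say which Day 1 summary is used and how many subjects lack it.

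The cost is a few sentences in 19.1 and a few lines of SAS, with no new data, visits or subjects. The downsides are a small loss of power if Day 1 burden is unrelated to resolution, and the loss from the adjusted test of any subject without a Day 1 rating. The retained unadjusted test covers the latter.

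### The plan does not say how the pre-dose Day 1 saliva value enters the exploratory longitudinal models; adjusting for it would usually sharpen the cytokine and viral-load contrasts

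*Combined protocol and SAP*

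**What the plan says.** Section 3.0 (Exploratory Objective) sets out the quantitative saliva outcomes. The cytokine outcome is "Reduction as compared to baseline (Day 1) in salivary levels of cytokine/chemokine RNA and/or protein", for 17 named markers at days 3, 7, 14 and 28. The viral-load outcome is "Quantitative RT-PCR for SARS-CoV-2 virus in saliva sample at days 1, 3, 7, 14, 28 and 42"; it is not defined as a change, and Day 1 is among the listed days.

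Section 12.1 makes Day 1 a true baseline: "Collect a baseline sample of saliva prior to taking drug".

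Section 19.1 notes that the exploratory outcomes are longitudinal, then gives the whole of their analysis in one sentence: "Standard statistical techniques for the analysis of such outcomes, ex., mixed linear models, will be utilized". It names no fixed effects, covariates, baseline handling or contrast. Elsewhere in 19.1, baseline variables appear only in connection with descriptive summaries. Two general rules also apply: "All statistical tests will be two-sided and tested at a 0.05 nominal significance level", and "no method of imputation will be used for missing data".

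On allocation, 19.1 says: "Participants will be randomized to the intervention or control arm in a 2:1 fashion using a permuted block randomization scheme". No stratification factor is named. With 30 subjects in total and 20 on melatonin (section 19.2), the comparison is 20 v 10.

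**The concern.** A pre-dose value is planned for each subject, yet the plan does not commit to using it to improve the comparison. Three analyses that fit the present wording would not adjust for it:

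- Cytokines analysed as change from Day 1, with no Day 1 term. A chance difference between arms at Day 1 passes in full into the contrast.
- Viral load compared at follow-up only. The Day 1 information is unused.
- Day 1 placed among the repeated responses, with arm means free at every day. Including Day 1 as a response does not by itself adjust for it. With complete data the fitted contrast is still the raw follow-up difference or the raw change difference. The gain comes from holding the Day 1 means equal or conditioning on Day 1.

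Section 19.1 says the analyses are aimed at estimation to help plan later trials, so precision matters by the plan's own standard. The salivary cytokines are also the only inflammatory markers measured, and the hypothesis in section 2.2 is partly about inflammation. Leaving baseline handling open further allows it to be chosen after the data are seen.

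**Working it through.** **The plan's own precision figure.** Section 19.2 gives a standard error of at most 11 percentage points for a safety proportion with 20 subjects. sqrt(0.5 × 0.5 / 20) = 0.1118, or 11.2 points, which agrees after rounding. It is the only precision figure in the plan, and none is given for the saliva outcomes.

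**Inputs.** From the documents: 20 v 10 subjects, a pre-dose Day 1 value, and cytokines defined as change. Assumed, because the documents give neither an SD nor a correlation: equal SDs at Day 1 and follow-up, roughly normal values, complete data, and a Day 1 to follow-up correlation r of 0.3 to 0.7.

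**Chance imbalance at Day 1.** SE of the Day 1 difference = sqrt(1/20 + 1/10) = 0.387 SD. The 95% chance range is ±1.96 × 0.387 = ±0.76 SD.

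**Variance of the arm contrast at one follow-up day**, in units of SD² × (1/20 + 1/10):

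- follow-up only: 1
- unadjusted change: 2(1 − r)
- baseline-adjusted: (1 − r²) × (1 + 1/(30 − 4)) = (1 − r²) × 27/26, where the last factor is the cost of estimating one covariate slope with 30 subjects

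Each SE is 0.387 times the square root of the variance. For r = 0.3: change 0.387 × sqrt(1.4) = 0.458; adjusted 0.387 × sqrt(0.91 × 27/26) = 0.376.

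| r | SE, change | SE, follow-up only | SE, adjusted | Reduction v change | Reduction v follow-up only |
|---|---|---|---|---|---|
| 0.3 | 0.458 | 0.387 | 0.376 | 18% | 3% |
| 0.5 | 0.387 | 0.387 | 0.342 | 12% | 12% |
| 0.7 | 0.300 | 0.387 | 0.282 | 6% | 27% |

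A simulation of 20,000 trials at each r gave 0.457, 0.386 and 0.301 for change, 0.388, 0.386 and 0.384 for follow-up only, and 0.377, 0.341 and 0.282 for the adjusted contrast.

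**Where the gain stops.**

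- Against follow-up only: (1 − r²) × 27/26 < 1 requires r² > 1/27, so r above about 0.19. At r = 0.2 the SE gain is 0.2%; at r = 0 there is a loss of about 2%.
- Against change: (1 + r) × 27/26 < 2 requires r below 52/27 − 1, or about 0.93.
- Change against follow-up only: 2(1 − r) > 1 when r < 0.5, so below 0.5 an unadjusted change score is noisier than ignoring Day 1 altogether.

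**The case against.** The strongest reply is that the plan is silent and has not chosen badly. Mixed linear models are offered as an example. The same sentence must also cover the binary detectable/undetectable outcome, which a linear mixed model would not ordinarily fit, so it cannot be read as a full model. A Day 1 covariate or a common Day 1 mean would fit the present text without contradiction. This stands: a reader might infer that the plan has decided not to use Day 1, and the documents do not support that.

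Defining the cytokine outcome as a reduction does not settle the model either. With Day 1 as a covariate, analysing the change or the follow-up value gives the same arm contrast. This also stands, but the equivalence holds only once the Day 1 term is present, and the plan does not mention one.

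For viral load, the change-score criticism does not apply. That outcome is not a change, and listing Day 1 may simply be the sampling schedule. Nor is viral load an inflammation marker. For this outcome only the risks of an unadjusted follow-up value or free Day 1 means remain.

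The size is uncertain. One range of r has been assumed for 17 markers and for viral load as late as Day 42. SDs may differ between days, and the formulas do not cover non-detects. At r = 0.3 the gain over follow-up only is 3%. These limits stand and are carried into the conclusion.

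Finally, the outcomes are exploratory, in a 30-subject pilot whose intervention arm was sized on safety: "the sample size of 20 in the intervention group is based on the expected precision". That limits the importance of the point, but the remedy is still nearly free.

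**Conclusion.** The point holds as a minor improvement. The plan should state how Day 1 enters the saliva models, because the cytokine outcome taken as written, without a Day 1 term, gives a noisier contrast than the planned data allow. Under equal SDs and r between 0.3 and 0.7, adjustment lowers the SE by about 18% to 6% against change and 3% to 27% against follow-up only. Little or nothing is gained over follow-up only below about 0.2, or over change above about 0.93. The true correlations cannot be found from the documents.

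A reader might go further and infer that adjustment is always better, or that the pilot's conclusions are undermined. Neither follows. The gain is not universal at this sample size, the plan makes no power or precision claim for the saliva outcomes, and no stated sample size or primary or secondary result changes.

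**What to change.** In section 19.1, state that quantitative viral load and each cytokine are analysed by a longitudinal model with a common Day 1 mean in both arms and arm-by-day effects only after Day 1. The alternative is to enter the Day 1 value as a covariate with a day interaction. In either case, report the adjusted arm difference at each follow-up day. The cytokine result can still be presented as a reduction from Day 1.

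The cost is wording plus about one degree of freedom per analysed day; no new samples or visits are needed. The common-mean form has the further merit of keeping subjects whose Day 1 sample is missing, which suits a plan that rules out imputation.
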